Screening	assessment						
Intervention	2. Randomization to:						
	
 
a. Intervention: study intervention with weekly coaching support in person and/or by phone x 12 week
 
						

	b. Comparison: one-time diabetes education session				
Follow-Up	3. Follow-up 1: 12-16-week follow-up assessments and A1c				
	Follow-up 2: 24-30-week follow-up assessments and A1c				
Efficacy Evaluations	• Satisfaction with trial, recruitment, retention rates				
	
 
Hemoglobin A1c measured by point-of-care fingerstick or venipuncture
 
				
	Self-reported medication adherence				
	Self-reported psychological wellness				
	Self-reported diabetes self-management, distress				
	
 
Height, weight, blood pressure
 
				
Safety Evaluations	Subject safety will be monitored by adverse events and rates of early termination of the study. We will also follow safety protocols in case we identify dangerous blood pressure values during assessment visits				
Statistical And Analytic Plan	We hypothesize a satisfactory, feasible, acceptable intervention with adequate recruitment and retention rates. We may see early indicators of improvement in efficacy measures of adherence, glycemic control, and wellness among intervention participants compared to comparison.				
	We will consider the study feasible if we screen 50% of those referred, enroll 75% of those screened who meet inclusion criteria, and 75% of participants complete follow-up. We will consider 70% session attendance as indicative of feasibility. We will consider the intervention				
	acceptable if 70% of participants are satisfied and would recommend it to others.				
	We will use generalized linear models to compare changes in A1c and medication adherence over time in intervention vs. comparison groups according to the ARMS-D measure of diabetes medication adherence while controlling for baseline differences and changes in housing status over time. Adherence will also be examined with pharmacy refill data (continuous medication gap for non-insulin diabetes medications 0-1.0). We will use an intention-to-treat approach including all randomized participants; multiple imputation will generate data for those lost to follow-up. Similar modeling approaches will compare psychological wellness, and other biometric and patient-reported outcomes.				

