Existing evidence-based models targeting medication adherence to improve diabetes will be the starting point for our novel intervention. We will draw from such interventions which target patient and system-level factors to improve diabetes self-care activities, including medication adherence, for historically disadvantaged groups. The overarching theoretical model guiding treatment development is the **Information** Motivation Behavioral Skills model. Our proposed treatment is also consistent with the Collaborative Care Model, a care management approach designed for individuals with multiple chronic conditions with known success improving diabetes outcomes in patients with depression. 45,46 The Collaborative Care Model frequently uses Motivational Interviewing as the counseling approach, as we plan to in this study. **Behavioral Activation (BA)** is another counseling approach that complements motivational interviewing. Behavioral intervention is empirically supported to address medication adherence in a population with high levels of underlying psychiatric disease (especially depression) and/or psychosocial stress. 96-99 BA is easier to train than other empiricallysupported counseling treatments and can be delivered with fidelity by bachelor's level practitioners. 100-101 BA is appropriately complemented by motivational interviewing, a person-centered, evidence-based approach to behavior change focused on participants' values and preferences and overcoming expected ambivalence to change. 48 It is particularly appealing to groups with historic disadvantage and minority race, 48 including the

homeless, and has improved medication adherence in non-homeless people with diabetes including when delivered by trained, non-mental health professionals to low-income populations. We will use BA first and employ MI when participants demonstrate ambivalence to change.

We will also integrate education using content consistent with the latest diabetes care guidelines. And we will offer problem-solving to address psychosocial needs (including food and housing) modeled after clinic-based approaches for homeless veterans. These evidence-based interventions offer a starting point for a new intervention which will be tailored to the unique context of DH through the iterative, multi-stakeholder process described below.

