### 5.2 Study Intervention

For participants randomized to the intervention group, they will be offered 10 coaching sessions over 12 weeks. These will be conducted in-person, via secure video, and/or by phone-based per participant preference and COVID-19 safety protocols. The treatment will center on providing diabetes education, motivational and goal-setting support, and resource and care coordination (Figure 2).

In-person assessment visits will be conducted at private spaces convenient to the participant including Hennepin Healthcare, Health Care for the Homeless sites, or at participant homes (see *Home Visit Protocol*).

All in-person assessment and treatment visits will follow current guidance from HHRI and Hennepin Healthcare about social distancing and use of personal protective equipment.

In-person treatment visits will be arranged that may include the participants home

Video visits will be conducted via a secure Zoom or Teams link (using HHRI, Hennepin Healthcare, and/or Hennepin County HIPAA secure technology) or Facetime if the participant is using an Apple device.

Phone visits will be conducted via a study or office phone or the PI's work phone. If participants have no working phone, a study phone will be issued to participants and will sign a Study Issued Cell Phone/Tablet Agreement (See *Phone/Tablet Agreement*).

Psychological approaches of behavioral activation and motivational interviewing will be used along with provision of educational materials and tools to support behavior change (See *Tools and Education Materials*). Coaches will tailor which tools and educational materials are given to which participants depending on participant need as well as the specific goals that are mutually set. E.g.) A participant with 10 medications per day may benefit from a pillbox with AM and PM slots. E.g.) A participant with many appointments for behavioral and physical health care may benefit from a pocket calendar. Financial value of tools ranges from \$4.99 (glucose log book) to \$17.91 (Adhesives for Continuous Glucose Monitor).

Approved communication channels will be used to support participant's goal setting (e.g. reminders) and arrange study related visits.

Participants will be offered up to 10 treatment visits over 12 weeks and monthly booster calls from weeks 12-24.

#### 5.2.1 Visit 1

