### 5.2.7 Comparison Group

Participants randomized into the comparison group will receive one 15 to 30-minute diabetes education session. Interventionists (coaches) will read the content of 3 diabetes educational handouts about (1) general descriptions of type 2 diabetes, (2) healthy eating, and (3) physical activity. Handouts are produced in alignment with American Diabetes Association guidelines by a community group (https://learningaboutdiabetes.org/) and have been used in previous diabetes behavioral trials with participants in low-income situations. Participants will receive a standard pillbox at this visit. Participants will receive a resource sheet with referral information to establish health care, mental health support, or to access local resources for housing, food, and other basic needs.

Comparison group participants will be contacted by the study staff (non-interventionists) once-monthly starting 4 weeks after their education session through the final assessment visit. Booster calls will update participant contact information and remind them of the timeline for follow-up assessments.

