#### 7 STATISTICAL CONSIDERATIONS

# 7.1 Primary Endpoint

The primary endpoint of this study is the satisfaction of participants in this pilot randomized trial (via CSQ-8).

The feasibility and acceptability of study protocols for recruitment, retention, and randomization are also important. We will assess this by measuring our ability to recruit and retain participants, and the assessment and treatment visits we can deliver (i.e., participant's attendance and follow-up with scheduled sessions and treatment activities). In addition to above outcomes, we will carefully track the number and types of between-treatment communications with participants (who initiated communication; form of communication: text, calls, e-mails, etc.).

We will consider the study feasible if we enroll 75% of those screened who meet inclusion criteria, and 75% of enrolled participants complete at least one follow-up. We will consider 50% session attendance as indicative of feasibility. We will consider the intervention acceptable if 70% of participants are satisfied and would recommend it to others.

We will also analyze our primary clinical endpoint of change in A1c between intervention and comparison groups between baseline follow-up visit #1 (approx. 12-16 weeks)

if it changes from baseline to between intervention.

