# 7.2 Secondary Endpoints

Secondary endpoints will include the following changes from baseline to follow-up visit #1 (approx. 12-16 weeks) between intervention and comparison groups.

- Psychological wellness (SF-12, MHI-5)
- Adherence to diabetes medications (ARMS-D) (secondary)
- Adherence to all medications (ASK-12) (secondary)
- Diabetes self-care (DSMQ) (secondary)
- Difficulties with diabetes management (PAID) (secondary)

Secondary endpoints will also include change from baseline to follow-up visit #2 (approx. 24-30 weeks) of A1c to assess sustained change of our primary endpoint.

We will also complete exploratory analyses on the change from baseline to follow-up visit #2 of:

- Adherence to diabetes medications (ARMS-D)
- Adherence to all medications (ASK-12)
- Diabetes self-care (DSMQ)
- Difficulties with diabetes management (PAID)

Exploratory analyses will further measure changes from baseline to follow-up visits #1 and #2 of other self-reported and claims-measures will be assessed including housing status, substance use, and other biometric measures (BP, BMI). Exploratory analyses will also compare self-reported adherence measures (ARMS-D and ASK-12) to measures built from medication refill patterns in insurance claims.

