# 7.4.1 Efficacy Analysis

We will use summary statistics (mean, standard deviation) to examine CSQ-8 scores for all participants. We will use t-tests to examine the differences in CSQ-8 scores between the intervention and comparison groups; we hypothesize no difference. We will also examine the experiences of White vs. Black, Native American, and Hispanic participants. We will also generate summaries of the age, gender, and race/ethnicity of people at the highest and lowest quintiles of CSQ-8 scores.

We will use generalized linear models to compare changes in A1c and medication adherence (ARMS-D and ASK-12) over time in intervention vs. comparison groups. We will control for baseline differences and changes in housing status over time. Adherence will also be examined with pharmacy refill data which we will compare to self-report (ARMS-D and ASK-12). We will use an intention-to-treat approach including all randomized participants; multiple imputation will generate data for those lost to follow-up. Similar modeling approaches will compare psychological wellness, blood pressure, and health care use outcomes.

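### The A1c and adherence models adjust for housing change after randomisation, so the arm difference need not be the effect of assignment to D-HOMES

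*Combined protocol and SAP*

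**What the plan says.** Section 7.4.1 specifies generalized linear models for A1c, ARMS-D and ASK-12 by arm, and adds: "We will control for baseline differences and changes in housing status over time". The Statistical and Analytic Plan in the synopsis has the same adjustment: "while controlling for baseline differences and changes in housing status over time". Section 7.4.1 extends similar models to psychological wellness, blood pressure and health care use. It also states: "We will use an intention-to-treat approach including all randomized participants", with multiple imputation for those lost to follow-up.

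Section 7.1 gives A1c its standing: "We will also analyze our primary clinical endpoint of change in A1c between intervention and comparison groups".

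On housing itself:

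- Table 1 schedules current housing status at baseline visit 1 and at both follow-up visits.
- Section 7.2 includes among its exploratory change outcomes "housing status, substance use, and other biometric measures (BP, BMI").
- Section 2 (Significance) says of the programme: "we will offer problem-solving to address psychosocial needs (including food and housing"). Section 5.2 says: "The treatment will center on providing diabetes education, motivational and goal-setting support, and resource and care coordination".
- Section 5.2.7 gives the comparison arm one education session and a resource sheet with referral information to "access local resources for housing, food, and other basic needs". Section 5.3 has staff point that arm back to the handout when a need is expressed.
- Sections 4.2 and 9.1.1 stratify randomisation by housing type, so a pre-randomisation housing variable already exists.

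**The concern.** Randomisation makes the arms comparable on everything fixed beforehand. A covariate measured afterwards does not have that protection. If assignment changes it, conditioning on it takes part of the treatment effect out of the arm coefficient. Here the same variable is an outcome in section 7.2 and an adjustment covariate in section 7.4.1.

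The coefficient is not a clean direct effect either if housing change and A1c share causes, such as mental illness or substance use. Conditioning on housing then links assignment to those causes and can produce an arm difference where none exists.

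No section gives a model without housing change or labels this one a mediation or sensitivity analysis. The adjusted coefficient is therefore the only specified estimate for the primary clinical endpoint and for the adherence and wellness outcomes. The plan means these measures to prepare a fully powered trial, so the model could carry forward into it.

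The term for baseline differences is also loose. The text does not say whether the baseline value of the outcome or the randomisation stratum is in the model.

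**Working it through.** The plan states no figure on this point to reproduce. It gives N = 54 and 1:1 allocation, with no SD, effect size or housing effect. Everything below except N and the allocation ratio is an assumption.

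**1. Is the covariate post-randomisation?** Randomisation takes place at or after baseline visit 2 (sections 4.2 and 9.1.1). Current housing is measured at baseline visit 1 and at follow-up visits 1 and 2 (Table 1). Change in housing therefore uses values recorded after allocation.

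**2. No shared cause of housing and A1c.** Let *d* be the A1c reduction not running through housing, *s* the arm difference in the proportion whose housing improves, and *e* the A1c reduction per housing improvement.

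- Effect of assignment = −(*d* + *s*·*e*)
- Housing-adjusted coefficient = −*d*
- Amount removed = *s*·*e*; share removed = *s*·*e* / (*d* + *s*·*e*)

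| *d* | *s* | *e* | Removed | Share |
|---|---|---|---|---|
| any *d* > 0 | 0 | any | 0 | 0% |
| 0.5 | 0.10 | 0.5 | 0.05 | 0.05/0.55 = 9.1% |
| 0.5 | 0.30 | 1.0 | 0.30 | 0.30/0.80 = 37.5% |
| 0.3 | 0.10 | 0.5 | 0.05 | 0.05/0.35 = 14.3% |
| 0.3 | 0.30 | 1.0 | 0.30 | 0.30/0.60 = 50% |

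**3. With a shared cause.** This was simulated with at least 2,000,000 subjects per scenario. *U* is standard normal. Housing improvement *M* follows a probit on arm and *U*, with 30% improving in the comparison arm. The link from *U* to *M* is 0.5 or 1.0, so improvers differ from non-improvers by roughly 0.7 or 1.2 SD of *U*. A1c change = −*d*·arm − *e*·*M* − 0.5·*U*. The sign matters: *U* is assumed both to improve housing and to lower A1c.

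Adjusted arm effect when the truth is no effect (*d* = 0, *e* = 0):

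| Housing shift by arm | Link 0.5 | Link 1.0 |
|---|---|---|
| 0 | 0.00 | 0.00 |
| 5 points | +0.02 | +0.03 |
| 10 points | +0.04 | +0.06 |
| 20 points | +0.07 | +0.12 |

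With *d* = 0.3, *e* = 0.5 and a 20-point shift, the effect of assignment is −(0.3 + 0.20 × 0.5) = −0.40. The adjusted estimate is −0.30 with no shared cause, −0.23 with link 0.5 and −0.19 with link 1.0.

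If the sign of *U* on A1c is reversed, the same case gives −0.37 (link 0.5) and −0.41 (link 1.0). The two biases then largely cancel.

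**4. Scale against sampling error.** Half-width of the 95% CI = *t* × SD × √(1/n₁ + 1/n₂), for assumed SDs of 1.5 and 2.0.

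- 27 v 27: 2.007 × 1.5 × √(2/27) = 0.82; with SD 2.0, 1.09.
- 20 v 21: 2.023 × 1.5 × √(1/20 + 1/21) = 0.95; with SD 2.0, 1.26. The 41 is 75% of 54, rounded up. It is illustrative, because the 75% criterion in section 7.1 concerns at least one follow-up and the plan imputes missing values.

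**The case against.** **No total effect is promised.** The intention-to-treat sentence describes who is analysed, and no section states an estimand. That is a fair reading of the words. But analysing everyone as randomised is done in order to estimate the effect of assignment, and this covariate can defeat that.

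**The housing pathway is thin.** Housing problem-solving appears in the background section. In the session content (sections 5.2.1 to 5.2.5) housing is named only as a contextual factor to assess at visit 1, and problem-solving there concerns barriers to behaviour change. The coordination wording in section 5.2 does not name housing, and the comparison arm also receives housing referrals. This stands: the documents do not show that D-HOMES changes housing, so the point is conditional. The arms do differ in intensity of support (up to 10 sessions plus boosters against one session), and the plan itself thinks a housing change worth testing.

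**Housing predicts outcome and dropout.** Section 2 (Overview) reports lower engagement among the least stably housed. That supports using baseline housing as a covariate and follow-up housing in the imputation. It does not support conditioning the arm comparison on follow-up housing.

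**The baseline wording could mean baseline housing differences.** It could, and baseline housing would then already be in the model. The problem with the change term remains.

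**The pilot's conclusions barely depend on it.** This is largely right. The primary endpoint is CSQ-8, compared by t-test without this covariate. No feasibility or acceptability threshold uses the adjusted estimate, and efficacy is declared under-powered.

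**Conclusion.** The concern holds. As written, the only specified A1c and adherence models condition on a post-randomisation variable that assignment may affect. Their arm coefficient equals the effect of assignment only if housing does not shift by arm, or if opposing biases happen to cancel.

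Under the assumed ranges the loss is 0.05 to 0.30 A1c points without a shared cause. A spurious difference of about +0.02 to +0.12 appears under the null for shifts of 5 to 20 points, when the shared cause acts in the direction assumed. These sizes rest entirely on assumed inputs and are smaller than the pilot's sampling error. The flaw matters for the clinical estimates and for the model handed on to the later trial. It does not affect the CSQ-8 or feasibility findings. It should be fixed.

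**What to change.** In the synopsis and in section 7.4.1, replace the covariate wording with:

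> Each model will include treatment arm, the baseline value of the outcome, and the randomisation stratum (housing type as recorded at randomisation).

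State as well whether the two follow-up visits are modelled separately or jointly. If jointly, add visit and the arm-by-visit interaction.

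Analyse housing change only as an outcome, as section 7.2 already plans, or in a model labelled as exploratory mediation or sensitivity analysis. Include the stratum in the imputation model. Observed follow-up housing may stay there as an auxiliary variable, which keeps its value for predicting missing outcomes.

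The cost is analysis-plan wording. All the variables are already collected, and the housing-adjusted result can still be reported under its proper label.

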type 2 diabetes and avoidance of complications. Diabetes medication adherence is low in housed populations, and limited evidence suggests it is as low or lower among DH; adherence is highly correlated with all-cause hospitalization and mortality.  We will consider the study feasible if we enroll 75% of those screened who meet inclusion criteria, and 75% of enrolled participants complete at least one follow-up. We will consider 50% session attendance as indicative of feasibility. We will consider the intervention acceptable if 70% of participants are satisfied and would recommend it to others.  The goal of the current study is to conduct a randomized pilot trial of the D-HOMES program. D-HOMES is a coaching-based collaborative care intervention tailored to DH using behavioral activation, motivational interviewing and psychosocial support to improve medication adherence. We will compare this to brief diabetes education and referral to meet medical and psychosocial needs. Our team's central hypothesis is that medication adherence, glycemic control, health care use/cost will improve with D-HOMES more than in our comparison. This pilot trial is under-powered to assess efficacy and focuses on recruitment, retention, blinding, and randomization procedures.	Study Rationale	housing and/or homelessness; this includes 44% of all adults seen at community health centers. The chronically homeless have a 5- to 10-fold increased risk of premature death and high health care costs (driven by acute emergency department and hospital visits). Diabetes prevalence is approximately the same among the homeless versus general population (8%), but people with type 2 Diabetes who experience Homelessness , herein abbreviated as DH , have worse glycemic control and are hospitalized for diabetes complications a decade earlier and with more frequency than their housed peers. Managing diabetes while homeless presents a unique set of barriers including food insecurity, low social support, lack of safe medication storage/refrigeration. Almost half of people who are				

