### 4.2 Allocation to Groups and Blinding

Participants will be randomized to either the intervention or a control group (1:1). Randomization will be stratified by housing type (unstable (e.g., shelter, staying outside) vs.

more stable (e.g., worry about rent payment, supportive or transitional housing)). Randomization will occur after baseline assessment visit #2 via REDCap. Staff who conduct who conduct the follow-up assessment visits will be blind to condition.

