# 4.3.2 Total Number of Study Sites/Total Number of Subjects Projected

Enrollment for the study will continue until 54 participants have been enrolled.

HHRI will serve as the only site for this study.

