#### 7.5 Sample Size and Power

This sample size is appropriate for the goal of feasibility and acceptability of the intervention. This is in line with ongoing studies by [name] (HSR#17-4351) as well as the current literature.

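### The A1c and adherence models do not name the outcome's baseline value as a covariate, and the adjustment wording leaves the covariate set open

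*Combined protocol and SAP*

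**What the plan says.** Section 7.1 makes participant satisfaction (CSQ-8) the primary endpoint and adds a "primary clinical endpoint of change in A1c between intervention and comparison groups", from baseline to the first follow-up visit. Section 7.4.1 plans generalized linear models for changes in A1c, ARMS-D and ASK-12, with similar models for other outcomes.

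On covariates, 7.4.1 has one sentence. It opens "We will control for baseline differences" and goes on to include change in housing status over the study. The synopsis, which names A1c and ARMS-D, has the same two terms: "while controlling for baseline differences", then the housing term. Section 7.4 plans only descriptive baseline summaries, and 7.3 names only the statistical support group.

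Table 1 schedules A1c, ARMS-D, ASK-12, DSMQ, PAID, SF-12 and MHI-5 at a baseline visit, and 4.2 places randomization after the second baseline visit. Section 4.2 also states "Randomization will be stratified by housing type", but the stratum is not mentioned as a model term.

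On size, 4.3.2 says "Enrollment for the study will continue until 54 participants have been enrolled", and 7.5 says "This sample size is appropriate for the goal of feasibility and acceptability of the intervention". The synopsis says "This pilot trial is under-powered to assess efficacy".

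**The concern.** Two analysts could fit different models from the one sentence in 7.4.1. One would always include the baseline value of the outcome. The other would inspect the baseline table and adjust for whatever looked different. In a randomized trial such differences arise by chance, so the second approach makes the model depend on the draw. When the arms look balanced on the outcome, it leaves an unadjusted change score.

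Two things are at stake. The first is prespecification: the covariates should not be open to choice once the data are in. The second is precision. Section 6.2 says these measures are collected to prepare for a later, fully powered trial. With 54 people and a 75% follow-up target (7.1), about 0.75 × 54 = 40 may be observed, so avoidable width in the intervals matters. The baseline values are already being collected.

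**Working it through.** **The plan's own figure.** The total of 54 cannot be reproduced, because no alpha, power, effect size or SD is attached to it. There is no stated power to test, so the check compares two analyses of the same data.

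**Inputs.** From the documents: 54 participants, 1:1 allocation (27 per arm), 75% follow-up target (20.25 per arm). Assumed: baseline to follow-up correlation r from 0.3 to 0.8, equal SDs at the two visits, two-sided 5% level, 80% power.

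**Variance.** In units of the outcome variance:
- unadjusted change score: 2(1−r)
- ANCOVA on baseline: 1−r²
- ratio: (1−r²)/[2(1−r)] = (1+r)/2

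The extra degree of freedom multiplies the ratio by about 1+1/50 with 54 people, or 1+1/36 with 40. The detectable difference is √(2/n) × (1.960+0.842) × √(variance factor). At n = 27 the first two terms give 0.762 SD.

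| r | Change | ANCOVA | Ratio | Ratio after df, N=54 / 40 | 54 × ratio | Detectable difference in SD, 27 per arm: change / ANCOVA | Same, 20.25 per arm |
|---|---|---|---|---|---|---|---|
| 0.3 | 1.40 | 0.91 | 0.65 | 0.66 / 0.67 | 35.1 | 0.90 / 0.73 | 1.04 / 0.84 |
| 0.5 | 1.00 | 0.75 | 0.75 | 0.77 / 0.77 | 40.5 | 0.76 / 0.66 | 0.88 / 0.76 |
| 0.7 | 0.60 | 0.51 | 0.85 | 0.87 / 0.87 | 45.9 | 0.59 / 0.55 | 0.68 / 0.63 |
| 0.8 | 0.40 | 0.36 | 0.90 | 0.92 / 0.93 | 48.6 | 0.48 / 0.46 | 0.56 / 0.53 |

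The column 54 × ratio is the number of participants with whom ANCOVA would match 54 unadjusted change scores, before the degree-of-freedom correction.

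**If the SDs are not equal.** Let b be the slope of follow-up on baseline and s₀ the baseline SD. The change-score variance exceeds the ANCOVA variance by (1−b)²s₀², which is never negative. The A1c entry threshold of 7.5% at baseline visit 1 (4.5.1) narrows s₀ and leaves b and the residual variance unchanged if the relation is linear. If it cuts the baseline variance to a fraction k, the ratio becomes (1+r)/[(1+r)+(1−r)k], with r the correlation before truncation. For an illustrative k = 0.5, this is 1.3/1.65 = 0.79, 1.5/1.75 = 0.86, 1.7/1.85 = 0.92 and 1.8/1.9 = 0.95. For A1c the gain may therefore be smaller than the table shows.

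**Adjusting only on observed imbalance.** This was simulated with 10,000 trials per r, 27 per arm, no true effect, and baseline entered only when the arms differed on it at p<0.05. That threshold is an assumption; the plan gives none.

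| r | Variance: change | Imbalance-driven | ANCOVA | Share of gain recovered | Type I error, imbalance-driven |
|---|---|---|---|---|---|
| 0.3 | 0.1006 | 0.0925 | 0.0675 | 0.0081/0.0331 = 24% | 3.6% |
| 0.5 | 0.0743 | 0.0696 | 0.0567 | 0.0047/0.0176 = 27% | 4.5% |
| 0.7 | 0.0446 | 0.0428 | 0.0387 | 0.0018/0.0059 = 31% | 4.6% |

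The rule recovers about a quarter to a third of the gain. It did not inflate type I error with this single covariate. Choice among several covariates was not simulated.

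**If baseline is always in the model.** With baseline B, follow-up Y and arm A, the model Y−B = a + tA + cB rearranges to Y = a + tA + (c+1)B. The arm effect t is the same whether change or follow-up is modelled, so the loss is zero.

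**The case against.** The strongest reply is that the plan states no selection rule. It has no baseline significance test and no threshold, and an ordinary reading is that baseline values are in the model. On that reading there is no loss of precision and the point is a request for clarity. This stands, and it is why the loss is stated conditionally. It does not remove the point, because the text does not say which reading is meant.

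A reader might also infer more than the documents support:
- **That baseline differences are the only adjustment.** They are not; the same sentence adds change in housing status.
- **That the baseline information is discarded.** A change score uses it, though inefficiently. With equal SDs it is better than ignoring baseline when r exceeds 0.5, equal at 0.5 and worse below.
- **That false positives are inflated.** The one-covariate simulation shows no inflation.
- **That the trial loses power it relies on.** It claims none for efficacy. Its primary objective (3.1) concerns satisfaction, recruitment, retention and the comparison-group process, and 54 rests on feasibility.

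These limits set the weight. They are not reasons to leave the sentence as it is.

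**Conclusion.** The point holds as one of prespecification and precision, at moderate weight. The plan models change, does not name the baseline outcome value as a covariate, and uses a phrase that fixes no covariate set. If baseline is omitted, ANCOVA would cut the variance of the arm difference by 35%, 25%, 15% or 10% at r of 0.3, 0.5, 0.7 or 0.8, less a few percent for the extra degree of freedom. These figures rest on an assumed r and equal SDs, and the A1c entry threshold could make the A1c gain smaller. If baseline was always intended, the loss is zero and the change only writes the intention down.

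Change in housing status needs settling in the same edit. It is measured after randomization, and the intervention includes help with psychosocial needs including housing (Section 2), so it could itself be affected by arm.

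**What to change.** Replace the whole covariate sentence in 7.4.1, and the matching clause in the synopsis, with:

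> The follow-up value (or change) of each outcome is modelled with arm, the baseline value of the same outcome, and the housing randomization stratum as fixed covariates. No covariate is selected from observed baseline imbalance. The arm difference is reported with its 95% CI. Change in housing status, which is measured after randomization, is used only in a sensitivity analysis.

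Apply this to A1c and to every patient-reported outcome with a baseline measurement. CSQ-8 has none in Table 1.

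For A1c, also state which baseline visit supplies the value. Table 1 marks A1c at both baseline visits, while 9.7.2 places blood draws at visits 1, 3 and 4.

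The cost is a few sentences, one or two degrees of freedom per model, and no new data. The edit should be made before outcome data are analysed.
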